**Safety Population**

The Safety population includes all participants who received at least one dose of study drug and will be analysed and presented according to the actual on-treatment monitoring arm received during the study.

The ITT population will be used for primary efficacy analyses, and the safety population will be used for all safety analyses.

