### **10.4 Assessments of safety**

#### ***Safety endpoint:***

8. Proportion of patients with common adverse events (reported in greater than 5%).
9. Proportion of patients with at least one severe or potentially life threatening (grade 3 or 4) adverse event.
10. Proportion of patients with un-scheduled clinic visits.

Safety analyses will also be undertaken with the proportion of patients with Grade 3 or 4 adverse events, and grade adverse events will be summarised by randomised treatment group, by severity and relation to study drug. Serious adverse events will be summarised for all enrolled patients.

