### **10.5 Definition of Intent-to-treat Population**

Intent-to-treat (ITT) and modified intent-to-treat (mITT) populations will be used for efficacy analyses. All patients who receive at least one dose of study drug will be included in the ITT population (and safety population). The mITT population will exclude patients who have completed treatment (>95% adherence) (according to phone contact at week 8), but have not returned for their SVR12 assessment. The data from the ITT and mITT will be presented by the treatment arm assigned at the time of randomisation. For the primary analyses of non-inferiority tests, the percentage of patients achieving SVR12 in each arm will be calculated with confidence intervals (CI) using the normal approximation to the binomial distribution.

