**Data Handling Conventions****Missing Data**

In general, missing data will not be imputed unless methods for handling missing data are specified. For the primary efficacy endpoint, participants with missing data will be analysed as missing equals failure.

Where appropriate, safety data for participants who did not complete the study will be included in summary statistics.

For example:

- If a participant took at least 1 dose of study drug, the participant will be included in a summary of adverse events according to the treatment received; otherwise, if the participant is not dosed, then they will be excluded from the summary.
- If safety laboratory results for a participant are missing for any reason at a time point, the participant will be excluded from the calculation of the summary statistics for that time point.

Values for missing safety laboratory data will not be imputed; however, a missing baseline (day 0) result will be replaced with a screening result, if available.

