### **Primary safety endpoint**

The primary safety endpoints are:

- Proportion of participants with common adverse events (reported by greater than 5% of the study population);
- Proportion of participants with at least one severe or potentially life threatening (grade 3 or 4) adverse event;
- Proportion of participants with unscheduled clinic visits.

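### The SAP groups safety by the monitoring arm received, the protocol groups adverse events by randomised arm, and no rule says which arm was received

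*SAP*

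**What the plan says.** SAP, Analysis Sets, Safety Population: everyone dosed is included, and the data are "analysed and presented according to the actual on-treatment monitoring arm received during the study". The scope is wide, since "the safety population will be used for all safety analyses". SAP, Missing Data, applies the same principle in its first example: once dosed, "the participant will be included in a summary of adverse events according to the treatment received". The introduction to the SAP's Safety Analyses section mentions grouping by arm without saying whether it means assigned or received.

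Protocol 10.4 points the other way: adverse events are to be "summarised by randomised treatment group, by severity and relation to study drug".

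The SAP keeps its ITT population by randomised arm. Its ITT and safety populations contain the same dosed participants, so one person could sit in one arm for efficacy and the other for safety.

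**The concern.** Grouping safety by treatment received is a sensible convention when arms take different drugs, because toxicity follows the drug swallowed. That reason does not apply here. What is randomised is a monitoring schedule, and the monitoring someone received is partly settled by behaviour after randomisation.

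Some of that behaviour may be a response to adverse events. Protocol 6.1 (Unscheduled visits) names adverse events and early treatment discontinuation among the reasons for such a visit, and asks for one, where possible, when treatment stops. The SAP also lists "Proportion of participants with unscheduled clinic visits" as a primary safety endpoint. If an analyst took on-treatment clinic attendance as evidence that standard monitoring was received, a simplified-arm participant with a problem could be counted in the standard arm. Whether on-treatment visits can safely be dropped is central to what the trial will conclude, and an error in that direction would flatter the simplified strategy.

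**Working it through.** **1. The texts side by side.**

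| Item | Protocol | SAP |
|---|---|---|
| Who is in the safety set | All dosed (10.5) | All dosed (Safety Population) |
| Grouping of adverse events | Randomised arm (10.4) | Arm received (Safety Population; Missing Data) |
| Grouping of ITT | Assigned arm (10.5) | Assigned arm (ITT Population) |
| Rule for the arm received | None | None |

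The conflict rests on protocol 10.4. Section 10.5 fixes membership of the safety set, but its sentence on assigned arm names only the ITT and mITT data.

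**2. What could distinguish the arm received.** The drug and its 8-week duration are common to both arms (protocol 4.1). The differences are:
- clinic visits at weeks 4 and 8 with their procedures, in the standard arm only (4.1, 6.1);
- pregnancy tests done at home in the simplified arm and in clinic in the standard arm (6.1);
- drug supply: four weeks at baseline and four more at week 4 (standard), or eight weeks at baseline (simplified) (5.2, 8.4).

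The SAP does not say which of these decides, how many visits must be attended or missed, or whether an unscheduled visit counts.

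**3. Size if reassignment depended on events.** The plan gives no figure for this, so the following is an illustration. The planned arm sizes, 125 standard and 250 simplified, come from protocol 10.1. Assumed: a true event rate r, the same in both arms, and a share m of simplified-arm participants with an event counted as standard. Expected proportions are then:

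- simplified = 250r(1 − m) / (250 − 250rm)
- standard = (125r + 250rm) / (125 + 250rm)

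| r | m | Simplified | Standard | Difference (simplified − standard) |
|---|---|---|---|---|
| 5% | 0 | 12.5/250 = 5.0% | 6.25/125 = 5.0% | 0 |
| 5% | 10% | 11.25/248.75 = 4.5% | 7.5/126.25 = 5.9% | −1.4 points |
| 5% | 25% | 9.375/246.875 = 3.8% | 9.375/128.125 = 7.3% | −3.5 points |
| 5% | 50% | 6.25/243.75 = 2.6% | 12.5/131.25 = 9.5% | −7.0 points |
| 10% | 25% | 18.75/243.75 = 7.7% | 18.75/131.25 = 14.3% | −6.6 points |

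The true difference is zero in every row. Grouping by randomised arm returns zero in every row.

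**4. Effect on the primary analysis.** None. The stated power of about 80% reproduces: SE = √(0.96 × 0.04 × (1/125 + 1/250)) = 0.02147, and Φ(0.06/0.02147 − 1.96) = 79.8%. Safety grouping does not enter this calculation.

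**The case against.** A reader might infer that the SAP makes attendance decide the safety arm, so that bias is certain. The documents do not support that.

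- **Attendance is not stated as the rule.** Baseline dispensing is another possible reading. It is settled before any on-treatment event, so reassignment on that basis could not depend on one.
- **An unscheduled visit is not standard monitoring.** Standard monitoring means scheduled visits at weeks 4 and 8 with a set list of procedures. SAP Table 15 keeps a simplified-arm column for unscheduled contacts, which would make little sense if an on-treatment clinic visit removed the participant from that arm.
- **The reverse crossover is weak.** A standard-arm participant who missed both visits would not be dispensed the week 4 supply, and so, absent off-schedule resupply, would not have received the simplified eight-week strategy.
- **Scheduled ascertainment is common.** Adverse events at weeks 4 and 8 are collected by phone in both arms (protocol 4.2, 7.1.1).

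A reader might also build a much larger effect. Suppose 12/250 simplified and 6/125 standard participants have unscheduled clinic visits (4.8% each). Moving all 12 gives 0/238 against 18/137, or 0% against 13.1%. Those counts are invented, every attender is moved, and the event that triggers the move is also the outcome. It is an extreme case and should not be quoted as the likely size.

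All of these objections stand, and they limit the claim to a possible bias. They do not remove the conflict with protocol 10.4 or supply the missing rule.

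**Conclusion.** The concern holds as an inconsistency plus an undefined rule. The SAP departs from protocol 10.4 on how adverse events are grouped, in two places and without giving a reason. The usual justification for as-received grouping is absent because the drug is identical in both arms.

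The bias is potential. It needs reclassification to occur and to be driven by attendance or unscheduled visits. On those assumptions, with a true 5% event rate and 10% to 50% of simplified-arm cases moved, the false difference runs from 1.4 to 7.0 points in favour of simplified monitoring. It is zero if nobody is reclassified or if baseline dispensing decides. The SVR12 analysis, by randomised arm in the ITT population, is unaffected. This should be corrected before the analysis, but it does not threaten the primary conclusion.

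**What to change.** 1. SAP, Safety Population: state that safety is analysed in every dosed participant according to randomised monitoring arm, in line with protocol 10.4.
2. SAP, Missing Data, first example: replace the reference to treatment received with the randomised arm. Changing only the first place would leave the SAP inconsistent with itself.
3. List departures from assigned monitoring separately, by randomised arm.
4. If an as-received summary is wanted, label it supplementary and write down beforehand exactly what determines the arm received, including whether unscheduled visits count.

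The cost is a short text edit in two places and one listing. Sample size, power and data collection do not change.

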**Data Handling Conventions****Missing Data**

In general, missing data will not be imputed unless methods for handling missing data are specified. For the primary efficacy endpoint, participants with missing data will be analysed as missing equals failure.

Where appropriate, safety data for participants who did not complete the study will be included in summary statistics.

For example:

- If a participant took at least 1 dose of study drug, the participant will be included in a summary of adverse events according to the treatment received; otherwise, if the participant is not dosed, then they will be excluded from the summary.
- If safety laboratory results for a participant are missing for any reason at a time point, the participant will be excluded from the calculation of the summary statistics for that time point.

Values for missing safety laboratory data will not be imputed; however, a missing baseline (day 0) result will be replaced with a screening result, if available.

**Outliers**

Outliers will be identified during data management and data analysis process, but no sensitivity analyses will be conducted. All data will be included in the data analysis.

**Visit Windows****Definition of Study Day**

Study day will be calculated from the date of first dose of study drug administration and derived as follows:

- For post-dose study days: Assessment Date minus First Dose Date + 1
- For days prior to the first dose: Assessment Date minus First Dose Date

The last dose date of the study drug will be the end date entered in the Treatment Termination or Drug Administration eCRF.

If there are participants for whom the date of last study drug is unknown (lost to follow-up and not able to be contacted), the date of last dose will be estimated using the maximum of non-missing study drug start or stop dates, visit dates, and laboratory collection dates (post-treatment visits and unscheduled visits are not included).

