### **8.2 Packaging and labelling**

Glecaprevir/pibrentasvir 100mg/40mg tablets are packaged in bottles of 30 tablets. 3 bottles are required for 4 weeks of treatment, which includes an extra 2 days of treatment. 6 bottles are required for 8 weeks of treatment, which includes an extra 4 days of treatment.

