### **8.4 Dosage and administration**

The study drug is to be administered orally once a day (three tablets per day) with food. Each participant must be given instructions to maintain approximately the same daily dosing interval between study drug doses. Participants should be instructed to swallow the study drug tablets whole. Participants should be instructed to only remove the tablets from the bottle immediately prior to dosing.

For a missed dose of study drug, participants should be instructed to take the missed dose of study drug as soon as possible during the same day. However, no more than the daily dose of glecaprevir/pibrentasvir should be taken on any calendar day. Participants should be cautioned never to double the next dose with a missed dose of study drug under any circumstances.

Participants in the standard arm will be dispensed with four-week supply (three bottles) at the Baseline and Week 4 visits.

Participants in the simplified arm will be dispensed with eight-week supply (6 bottles) at the Baseline visit.

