### Analysis Windows

Participant visits might not occur on protocol-specified days. Therefore, for the purposes of analysis, observations will be assigned to analysis windows. In general, the baseline value will be the last non-missing value on or prior to the first dose date of study drug. HCV RNA and safety laboratory data collected up to the last dose date +  $\leq 3$  days are considered on-treatment data. HCV RNA and safety laboratory data collected after the last dose date +  $> 3$  days are considered post-treatment data.

The following days are based on treatment start date and stop date for the on and post treatment period, respectively.

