#### On-treatment

Nominal visit	Standard monitoring arm			Simplified monitoring arm		
	Nominal day	Lower Limit	Upper Limit	Nominal day	Lower Limit	Upper Limit
Baseline	1	NA	1	1	NA	1
Week 4	28	21	42	NA	NA	NA
Week 8	56	43	59	NA	NA	NA

\*The protocol specifies that the visit window for Week 4 and Week 8 is plus or minus 3 days.

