#### Post-treatment

Nominal visit	Standard monitoring arm			Simplified monitoring arm		
	Nominal day	Lower Limit	Upper Limit	Nominal day	Lower Limit	Upper Limit
PT week 12	84	70	NA	84	70	NA

\*The protocol specifies that the visit window for Post Treatment Week 12 is plus or minus 14 days. As the post treatment week 12 visit is the final scheduled study visit, the upper limit for the post-treatment week 12 visit will not be specified, and instead will be set at study close.

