**Figure 2. Participant disposition**

## **BASELINE DATA**

### **Demographic Data and Baseline Characteristics**

Demographic and baseline measurements will be summarized using standard descriptive methods (Table 6, Table 7).

Baseline data will be summarised for the ITT population and by study arm as: number (n) and proportion for categorical parameters; or n, mean and standard deviation (SD), median, Q1, Q3, minimum and maximum for continuous parameters.

Age will be calculated in years at the date of initial study drug administration (baseline).

*P* values will not be reported for differences between the two groups at baseline, since appropriate randomisation methods will have accounted for this. Any differences identified would be due to chance such that a significant *p* value would in reality be representative of a type 1 error. Large differences at baseline (more than half a SD for continuous variables or 10% for categorical variables) will be investigated in a sensitivity analysis.

Prevalence of baseline polymorphisms in NS3 and NS5A will be summarised (Table 8).

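### A standard-arm end-of-treatment HCV RNA result from the last permitted Week 8 visit day falls one day past the SAP's Week 8 limit and is assigned to no analysis window

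*SAP*

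**What the plan says.** - **Protocol visit days.** The Schedule of Assessments (Standard monitoring arm) puts baseline at day 0 and Week 8 (EoT) at day 56, with a window of 3 days either side. A local HCV RNA test is scheduled at that visit.
- **SAP day count.** Definition of Study Day gives "For post-dose study days: Assessment Date minus First Dose Date + 1", so the first-dose date is day 1. The window table lists baseline as nominal day 1, and Demographic Data and Baseline Characteristics treats baseline and first dose as the same date. The Missing Data section uses the other convention: "a missing baseline (day 0) result will be replaced with a screening result".
- **SAP Week 8 window.** The On-treatment table gives the standard arm nominal day 56, lower limit 43 and upper limit 59, counted from treatment start. Its footnote adds: "The protocol specifies that the visit window for Week 4 and Week 8 is plus or minus 3 days".
- **SAP last-dose rule.** Under Analysis Windows, results up to 3 days after the last dose are on-treatment. The companion sentence, beginning "HCV RNA and safety laboratory data collected after the last dose date", makes results more than 3 days after it post-treatment.
- **SAP post-treatment window.** There is one row, "PT week 12 84 70 NA": nominal day 84, lower limit 70, no upper limit, counted from the stop date.
- **Dosing and supply.** Treatment lasts 8 weeks. Protocol 8.4 says "The study drug is to be administered orally once a day (three tablets per day) with food", and Protocol 8.2 says "6 bottles are required for 8 weeks of treatment, which includes an extra 4 days of treatment".

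**The concern.** The SAP introduces analysis windows because visits may miss their planned days, and its other limits are generous. Week 4 runs from 21 to 42, Week 8 opens at 43, and post-treatment week 12 never closes. The Week 8 upper limit alone appears tighter than the visit window that the protocol permits, although the footnote beneath it cites that visit window.

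Week 8 is the one visit during treatment with a scheduled local HCV RNA test, and only the standard arm has it. The result fills the end-of-treatment row of Table 10 and helps to separate on-treatment failure from relapse in Table 11. If the stated rules leave a compliant sample unassigned, someone must decide what to do with it after seeing the result.

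**Working it through.** **Inputs.** Protocol schedule: baseline day 0, Week 8 at 56 ± 3. SAP: study day = assessment date − first dose date + 1; Week 8 window 43 to 59; on-treatment up to last dose + 3 days; post-treatment window from stop + 70 days. Protocol: one dose a day for 8 weeks, which is 56 dosing days.

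**1. Reproducing the SAP's 59.** It arises in two ways:
- protocol day 56 + 3 = 59 on the day-0 scale;
- 56 daily doses from SAP day 1 end on SAP day 56, and 56 + 3 = 59 on the day-1 scale.

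**2. Converting the permitted days.** With the first dose on the baseline date, SAP day = protocol day + 1. The permitted Week 8 days, protocol 53 to 59, become SAP 54 to 60. Day 60 exceeds 59.

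**3. Applying both SAP rules, with the last dose on SAP day 56:**

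| Protocol day | SAP day | In 43–59? | Days after last dose | Last-dose rule |
|---|---|---|---|---|
| 53 | 54 | yes | −2 | on-treatment |
| 56 | 57 | yes | 1 | on-treatment |
| 58 | 59 | yes | 3 | on-treatment |
| 59 | 60 | **no** | 4 | post-treatment |

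On the last row, 4 days after stopping is far short of 70, so the sample enters no post-treatment window either.

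**4. Varying the last dose, with the visit on protocol day 59 (SAP day 60).** Six bottles of 30 tablets at three a day last 6 × 30 / 3 = 60 days, so a last dose as late as SAP day 60 is possible.

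| Last dose (SAP day) | Days after last dose | Last-dose rule | Week 8 window |
|---|---|---|---|
| 56 | 4 | post-treatment | none |
| 57 | 3 | on-treatment | none |
| 58 | 2 | on-treatment | none |
| 60 | 0 | on-treatment | none |

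From day 57 onward the two rules disagree about the same sample.

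**5. Varying the first dose.** If it is taken the day after baseline, protocol day 59 is SAP day 59. The sample is inside the window and the gap closes.

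**6. SVR12.** The visit is at protocol day 140 ± 14, which is 126 to 154. The planned last dose is protocol day 55, so the visit falls 126 − 55 = 71 to 154 − 55 = 99 days after it, all beyond 70. A later last dose shortens these intervals day for day, but that concerns the 70-day limit. The Week 8 limit plays no part in SVR12.

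**The case against.** The best defence is that 59 is not a slip. On the SAP's own scale it is the planned last dose day plus the 3 days allowed by the last-dose rule, and nominal day 56 is the planned last treatment day. On that reading, excluding a sample taken 4 days after treatment is deliberate. This stands as to origin: a reader might infer that 59 was carried over from the day-0 schedule, but the documents do not settle it. It does not remove the gap. Whatever its origin, the limit excludes a visit day that the protocol permits, and it also excludes day-60 samples that the last-dose rule calls on-treatment.

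Four stronger readings are tempting, and the documents do not support them:

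- **A quantifiable day-60 result would be counted as relapse.** Study Definitions sets virologic failure at 12 weeks after cessation and requires homologous virus on sequencing for relapse. The post-treatment label also depends on the actual last dose date. The label could mislead, but it does not decide the classification.
- **Week 8 safety laboratory data would be lost.** Safety Analyses covers data to 30 days after the last dose. Tables 19 and 20 use only baseline and post-treatment week 12, and the footnoted grades in Table 21 run to 30 days after treatment. Only a by-visit summary under Laboratory Evaluation, for which these shells have no Week 8 row, could lose the value.
- **No other on-treatment viral load could exist.** Standard-arm plasma is also stored at Week 4, and Protocol 9.1 includes HCV RNA testing among its uses.
- **About 18 results would drop out.** That is 125 / 7 = 17.9, which assumes that visits spread evenly over the seven days. Neither document gives an attendance pattern.

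**Conclusion.** The gap is real but narrow. With the first dose on the baseline date, a standard-arm end-of-treatment HCV RNA result from the last permitted visit day has no analysis window and is absent from the end-of-treatment row of Table 10. That row is descriptive, with no simplified-arm figure or between-arm comparison. Whether the sample is also called post-treatment depends on the last dose: yes if it was on or before SAP day 56; otherwise the last-dose rule and the window table conflict.

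The reach is one of seven permitted visit days, in one arm, for an unknown number of participants. The primary endpoint is untouched, and so are most safety tables. The conclusion rests on equating baseline with first dose, as the SAP does; a first dose one day later removes the gap. This is a minor correction, best made before database lock.

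**What to change.** Make two changes to the SAP together:

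1. In the On-treatment window table, set the Week 8 upper limit to 60.
2. In Analysis Windows, add an explicit exception to the last-dose rule: the scheduled Week 8/EoT sample, if taken inside the protocol visit window or within 3 days after the last dose, is the end-of-treatment value.

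The first change alone is not enough. With the last dose on day 56, a day-60 sample would sit in the Week 8 window and still be labelled post-treatment.

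Changing the nominal days to 29 and 57 would match the day-1 count but is optional, since it reassigns no observation. The day-0 label for baseline under Missing Data could be aligned at the same time.

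The cost is one number and one sentence, with no effect on visits, dosing or the primary analysis. The small downside is that a few end-of-treatment values will have been taken 4 days after the last dose; a footnote to Table 10 can say so.
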